Allowed rescue medications will be provided if subjects report a pain intensity score of ≥ 5 on the NRS and require additional analgesia in addition to PCA. For the first 2 hours after the start of the study drug infusion, subjects will be allowed to receive IV fentanyl up to 2 doses in 1 hour with the first dose of 30 µg and the second dose of 20 µg at a 10-minute lockout interval. If subjects request additional rescue medications exceeding allowed fentanyl administrations for 1 hour, IV Oxycodone (Oxynorm, 2 mg, 2-hour lock-out) or Morphine (Morphine Sulfate Injection, 2 mg, 2-hour lock-out) will be given. After 2 hours from the start of the study drug infusion, IV pethidine (25 mg, 4-hour lock-out) in addition to PCA will be administered upon request in the ward. If subjects experience inadequate pain relief despite the use of PCA opioids and protocol-specified rescue medications, they will be provided appropriate pain medications at the investigator's discretion.

Pain Intensity Assessment

Pain intensity will be assessed using the NRS (0-10) at scheduled time points for 48 hours from the start of the study drug infusion. When a subject requests rescue medications, the corresponding pain

5

intensity score at the time of request will be recorded using the NRS, and the rescue medication will be administered.

Dropouts

Subjects are free to discontinue from the study at any time, without prejudice to future treatment. Reasons for withdrawal or discontinuation from the study may include the following and must be documented in the eCRF: a lack of efficacy, safety criteria (e.g., adverse events, unexpected drug reaction), pregnancy, protocol deviations, and sponsor/investigator decision. Once a subject is discontinued from the study, no data will be collected except for the safety data.

Safety Follow-Up

After discharge, subjects will be contacted for a follow-up phone interview. Subjects may visit the site at any time during the study for the postoperative care depending on the judgment of the investigator or the condition of a subject, but this follow-up visit is not included as part of this study. A total duration of the study is approximately 21 to 30 days including a safety follow-up.

Efficacy Endpoints:

The primary efficacy endpoint

Time-weighted Sum of Pain Intensity Difference (SPID) from baseline over 12 hours after the start of the study drug infusion (i.e., post-dose).

The secondary efficacy endpoints

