- Total number of PCA requests for 12 hours post-dose
- Total amount of PCA and rescue medication consumption for 12 hours post-dose
- Proportion of subjects with ≥ 40% decrease in pain area at 6 hours post-dose compared to the maximum pain area with the pre-dose pain intensity
- Time-weighted SPID for 24 hours post-dose (SPID 24)

Exploratory endpoints

- Time-weighted SPID for 6 hours post-dose (SPID 6)
- Total number of PCA requests for 24 and 48 hours post-dose
- Total amount of PCA and rescue medication consumption for 24 and 48 hours post-dose
- Population of subjects with ≥40%, ≥60%, and ≥80% decrease in pain area at 12, 24, and 48 hours post-dose compared to the maximum pain area with the pre-dose pain intensity
- Proportion of subjects who have not requested any rescue medication between 0-2, 2-6, 6-12, 12-24, and 24-48 hours post-dose
- Time to the first and the second rescue medication requested by subject
- Pharmacokinetic (PK) profile of VVZ-149 Injections

Safety Endpoints:

Postoperative nausea and vomiting, 12-lead electrocardiograms (ECGs), vital signs, clinical laboratory evaluation (blood chemistry, hematology, blood coagulation, and thyroid testing), oxygen saturation, physical examination, and adverse events reported during the study.

6

Statistical Analysis:

The primary objective is to evaluate a pivotal assessment of the analgesic effects of VVZ-149 Injections in subjects with moderate to severe postoperative pain following laparoscopic colectomy. The secondary objectives include the extended analgesic efficacy, safety and PK of VVZ-149 Injections.

CONFIDENTIAL

General Statistical Considerations

Statistical analyses will be performed using SAS® Enterprise Guide (version 9.4) 64 bit (SAS Institute Inc., Cary, NC, USA) or higher.

Continuous variables will be summarized using descriptive statistics, including number of subjects (n), mean, median, standard deviation (STD), minimum and maximum. The mean and median will be reported to an additional level of precision than the original observation in its rawest form (i.e., electronic case report form, eCRF), and the STD and other measures of variability (e.g., standard error) will be reported to two additional levels of precision than the original observations. The minimum and maximum will be the same precision as the original data.

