Categorical variables will be summarized using counts of subjects (n) and percentages (%) and will be presented in the form "n (xx.x)". Percentages will be rounded to one decimal place. If counts of subjects is zero (0), then percentage will not be displayed. To ensure completeness, summaries for categorical variables will include all categories, even if no subjects had a response in a particular category. Unless otherwise specified, the denominator for each percentage will be based on the number of subjects with available data in the population being summarized.

Unless otherwise specified, all statistical tests will be 2-sided using α =0.05. Estimates and confidence intervals will be reported to 1 more decimal than the original data. P-values will be reported to 4 decimal places. Pvalues less than 0.0001 will be displayed as "< 0.0001"; p-values greater than 0.9999 will be displayed "> 0.9999". Summary tables will be summarized by treatment and overall, as appropriate. All data, including those derived, will be presented in individual subject data listings.

Demographic Data Analysis

The Modified Intent-to-Treat (mITT) population will be used for the analysis of demographic variables. Age, height, body weight and body mass index (BMI) will be summarized using descriptive statistics. Age group, sex, race and American Society of Anesthesiologists (ASA) risk classification will be summarized with the number and percentage of subjects in each parameter category.

Subjects who have not initiated the study drug infusion, or who do not have a baseline pain intensity score nor any post-dose pain intensity score will be excluded from the mITT population.

Descriptive statistics will be performed in all subjects and by treatment group. Continuous variables will be summarized using descriptive statistics (sample size, mean, standard deviation, minimum, median, and maximum values). Categorical variables will be summarized using the number and percentage of subjects.

Safety Analyses

- The Safety Population who have initiated study drug infusion will be used for all safety analyses. The occurrence, the number of subjects, severity, and relatedness will be summarized for adverse events (AEs) and serious adverse events (SAEs) using descriptive statistics.

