- All secondary efficacy analyses will be carried out using two-sided tests at the alpha = 0.05 level of significance. The total number of PCA requests and the total amount of opioid consumption by PCA and/or rescue medication at pre-defined time intervals until 12 hours postdose will be summarized and analyzed using a repeated-measures ANOVA. The main effects of treatment and time and their interaction (treatment x time) will be evaluated. The proportion of subjects with ≥ 40% decrease in pain area at 6 hours post-dose compared to the maximum decrease in pain area with the pre-dose pain intensity will be summarized and analyzed by treatment group using Chisquare test (or Fisher's test if the expected cell counts with less than 5 is greater than 20%). The same method described for the primary efficacy endpoint (ANOVA) will be used to analyze the time-weighted SPID for 24 hours postdose (SPID 24).
- All exploratory efficacy analyses will be carried out using two-sided tests at the alpha = 0.05 level of significance. SPID 6 will be analyzed using an ANOVA model with treatment as the main effect. The total number of PCA requests and the total amount of opioid consumption by PCA and rescue medication for 24 (at a 6-h interval) and 48 hours (at a 12-h interval) post-dose will be analyzed using a separate repeated measures ANOVA with the main effects of treatment and time and their interaction (treatment x time).

Proportion endpoints measured per time interval will be analyzed by treatment group using Chisquare test (or Fisher's test). Additional analysis will performed using a generalized linear model with repeated measures using a logit link.

The time-to-event exploratory endpoints (time to first and second rescue medications requested by subject) will be analyzed based on the Kaplan-Meier (KM) estimate of median time (in minutes) with log-rank test and Cox proportional hazard model with treatment as a factor.

Version Date: Jan. 27, 2023

Schedule of Assessments

Period	Screen	В	aseline	e		Treatment Dosing and Assessment													
Visit	1		2															3	
Study Day	-30to-1					1							2				2 to 3		21
Time Point		Pre op	Pre dose	0h ^a	0.5h	1h	2h	4h	6h	8h	10h	12h	18h	24h	30h	36h	42h	48h ET	
Time Point Window					±5 m ±10 m			±15 m			-30 m	±15n	±1 h					+7 d	
Informed consent	X																		
Inclusion exclusion criteria	X	Xb	X ^b																
Demographics	X																		
HADS/PCS ^r		X																	
Weight and height	X																		

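### The available-data denominator leaves subjects who quit before 6 hours for lack of efficacy or adverse events out of the secondary responder endpoint, instead of counting them as non-responders

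*Combined protocol and SAP*

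**What the plan says.** Under General Statistical Considerations, the paragraph on categorical variables sets a default for all percentages, which holds where no other rule is specified: "the denominator for each percentage will be based on the number of subjects with available data in the population being summarized".

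The secondary efficacy endpoints include "Proportion of subjects with ≥ 40% decrease in pain area at 6 hours post-dose compared to the maximum pain area with the pre-dose pain intensity". Under Efficacy Analyses, this proportion "will be summarized and analyzed by treatment group using Chisquare test", with Fisher's test as the fallback for small expected counts, at a two-sided 0.05 level. The endpoint list and Efficacy Analyses give no different denominator, no rule for subjects who leave early and no imputation rule.

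The Dropouts paragraph lists these reasons for leaving: "a lack of efficacy, safety criteria (e.g., adverse events, unexpected drug reaction), pregnancy, protocol deviations, and sponsor/investigator decision". It then states: "Once a subject is discontinued from the study, no data will be collected except for the safety data".

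The mITT population is used for efficacy. It excludes subjects who never started the infusion or who lack baseline and post-dose pain scores. A subject with a baseline score and at least one post-dose score stays in.

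**The concern.** A subject who leaves because the treatment did not work or was not tolerated has failed treatment. A responder endpoint can record that directly, without inventing a pain score. Under the available-data default the subject is neither a success nor a failure, but absent. Who is counted then depends partly on outcome after randomisation, so the two arms are no longer compared as randomised.

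At stake is one of four secondary endpoints. If more subjects leave early on active drug, the apparent benefit grows. If more leave on placebo, it shrinks. The same default reaches the exploratory 40%, 60% and 80% pain-area proportions at 12, 24 and 48 hours, where the longer windows give more time for subjects to leave.

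**Working it through.** **Does the rule reach these subjects?**

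1. Pain is scored pre-dose and at 0.5, 1, 2, 4 and 6 hours (Schedule of Assessments). A subject who leaves after, say, the 2-hour score has a baseline and post-dose scores, so is in mITT.
2. Only safety data are collected after discontinuation (Dropouts), so the 4- and 6-hour scores are missing and the 0–6 hour area is incomplete.
3. The only denominator rule is the available-data default. The subject leaves the percentage and the test built on it.
4. The PP set requires efficacy data to at least 6 hours, so it removes the same subjects. The FAS keeps anyone with efficacy data after randomisation but has no denominator rule of its own. No planned analysis counts these subjects as non-responders.

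**Size.** The documents give 300 subjects randomised 1:1, so 150 per arm. They give no responder rate, dropout rate or power calculation, so there is no planned figure to reproduce. The responder and leaver counts below are assumptions.

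Let r be responders, n = 150 and d those who leave before 6 hours, all of them failures.

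- Failures counted: r/n
- Available data: r/(n − d)
- Test: Pearson chi-square, two-sided, no continuity correction

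With r = 60 active and 45 placebo:

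| Leavers, active v placebo | Calculation | Rates | Difference (points) | p |
|---|---|---|---|---|
| Any, counted as failures | 60/150 v 45/150 | 40.0% v 30.0% | 10.0 | 0.069 |
| 3 v 3, dropped | 60/147 v 45/147 | 40.8% v 30.6% | 10.2 | 0.068 |
| 5 v 2, dropped | 60/145 v 45/148 | 41.4% v 30.4% | 11.0 | 0.050 (0.0502) |
| 15 v 5, dropped | 60/135 v 45/145 | 44.4% v 31.0% | 13.4 | 0.021 |
| 5 v 15, dropped | 60/145 v 45/135 | 41.4% v 33.3% | 8.0 | 0.165 |

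The result can also move from significant to not significant. With 63 v 45 responders, counting failures gives 42.0% v 30.0%, p=0.030. Dropping 6 v 15 leavers gives 63/144 v 45/135 = 43.8% v 33.3%, p=0.074. A smaller loss of 2 v 5 gives 11.5 points, p=0.041.

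**If there is no true difference.** Suppose both arms have a 40% responder rate with leavers as failures, and a fraction q leaves early. The available-data rate is 0.40/(1 − q).

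- 5% v 2% leaving: 42.1% v 40.8%, a spurious 1.3 points. The rejection rate is about 5.6% instead of 5%.
- 10% v 3% leaving: 44.4% v 41.2%, a spurious 3.2 points. The rejection rate is about 8.4%.

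These rejection rates use a normal approximation with unpooled variance.

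**The case against.** **The default is a reporting convention.** It sits among rules on rounding and zero counts, and it does not mention dropouts. A reader might infer that the sponsor chose to exclude treatment failures. The documents do not show that; the exclusion follows from a general default with no exception. But it is the only denominator rule given, and the same proportion is both summarised and tested. If it was not meant to govern, the plan has no rule for these subjects and needs the same sentence.

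**Scores may be imputed.** Efficacy Analyses speaks of pain scores being assigned from 0 to 12 hours. That hints at an assignment step, but it states no rule and concerns SPID 12 only.

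**An early-termination score is scheduled.** The last treatment column of the Schedule is headed 48h ET and includes a pain score. This conflicts with collecting only safety data after discontinuation, and the two must be reconciled. One such score still does not give the missing scheduled scores up to 6 hours.

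**Stopping the infusion is not leaving the study.** This stands. Schedule footnote k provides for infusions shorter than 10 hours, and such subjects can still give 6-hour scores. Inadequate relief leads to PCA, rescue and discretionary analgesia; no section makes it a trigger for withdrawal. Early leavers may therefore be few.

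**The large examples are extreme.** This stands too. A loss of 10% of one arm within 6 hours, with strong imbalance, has no support in the documents. The smaller losses are shown for that reason.

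**A stronger inference that fails.** A reader might infer that using whatever scores exist would turn an unrelieved early leaver into a responder, because a short pain area is set against a full 6-hour maximum. The plan does not give that formula. If the decrease is built from pain intensity differences, as SPID is, unchanged pain gives a decrease of zero and the subject is a non-responder.

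**Conclusion.** The concern holds for the 6-hour pain-area responder endpoint and, by the same default, for the exploratory pain-area proportions. As written, subjects who leave the study early for outcome-related reasons are omitted from the comparison, and no planned sensitivity analysis counts them as failures.

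The effect is small if few leave or if leaving is balanced: 0.2 points with 3 v 3 in the example. It becomes material with imbalance: 1.0 point with 5 v 2 and 3.4 points with 15 v 5, the latter moving p from 0.069 to 0.021. All of this rests on assumed counts.

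A reader might infer that the rule favours the active drug. The documents do not support that; the direction depends on which arm loses more subjects. Nor does the rule threaten the primary result, because SPID 12 is compared as a mean and has no such denominator. The four secondary endpoints are unranked, so this one should not be given special standing among them. The change should be made before unblinding, because the choice can move significance either way.

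**What to change.** In Efficacy Analyses, override the available-data default for the pain-area responder endpoints (6 hours, secondary; 12, 24 and 48 hours, exploratory):

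- Use all mITT subjects in the arm as the denominator.
- Count a subject who discontinues the study before the end of the window as a non-responder.
- Analyse subjects who stop the infusion but stay in the study on their observed scores.
- Report the available-data version as supportive.

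Also reconcile the early-termination pain score in the Schedule of Assessments with the Dropouts statement on data collected after discontinuation.

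The override costs one or two sentences and one extra table. Responder percentages will be slightly lower, and subjects who leave for unrelated reasons, such as a sponsor decision, will count as failures. The supportive analysis shows how much that matters. The change is not proposed for the interval rescue-free proportions, where calling every leaver a failure out to 48 hours is debatable.

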VVZ-149 (Opiranserin, INN) is a dual antagonist of GlyT2 and 5HT2A, which plays an important role in modulating the induction and transmission of pain signals via the central and peripheral nervous systems. GlyT2 antagonists reduce the reuptake of glycine that inhibits pain signals at spinal synapses, which depresses the transmission of pain signals toward the brain. 5-HT2A is expressed in the termini of descending facilitatory projection neurons in the midbrain and involved in the amplification of pain signals in the spinal dorsal horn. 5HT2A is also expressed in the termini of peripheral nociceptive neurons (a start point of postoperative pain) and generates pain signals. Thus, 5-HT2A antagonists inhibit facilitatory pain signals and activation of nociceptive receptors, which reduces the sensation of pain. VVZ-149 has demonstrated comparable efficacy to morphine in well-controlled (blind, complete randomization with a positive control) animal studies using rat models of postoperative pain and formalin-induced pain.

Two Phase 1 studies (PT-VVZ149-01/02), five Phase 2 studies (PT-VVZ149-04/05, VVZ149-POP-P2-US001/US002/US004), and one Phase 3 study (VVZ149-POP-P3-US003) have been completed in Korea and the US to evaluate the efficacy, pharmacokinetics (PK) and safety of VVZ-149 Injections (Unafra, Brand name) for treating postoperative pain. Clinical trials with a continuous 8 to10-hours IV infusion of VVZ-149 Injections administered pre-, during-, and postoperatively demonstrated effective analgesia using VVZ-149 Injections with substantially reduced opioid consumption compared to the placebo. The most frequent adverse events (AEs) reported were nausea, vomiting, headache, dizziness, and somnolence, and to date, there have been no other clinically significant AEs, which indicates the excellence in safety and drug tolerance of VVZ-149 Injections.

OBJECTIVES:

Primary Objectives:

To make a pivotal assessment of the analgesic effects of VVZ-149 Injections (1000 mg VVZ-149 for 10 hours, administered as a loading dose of 160 mg for 30 minutes followed by a maintenance dose of 840 mg for 9.5 hours) for treating postoperative pain following laparoscopic colectomy.

Secondary Objectives:

To evaluate (1) the extended analysesic effects and reduced postoperative opioid requirements by VVZ-149 Injections, and (2) the safety and tolerability of VVZ-149 Injections up to 48 hours postdose

Version Date: Jan. 27, 2023

Subjects:

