- Vital signs, 12-lead ECGs, and clinical laboratory evaluations per group will be summarized using descriptive statistics, and further statistical analyses will be performed regarding indices considered clinically significant as necessary.

Efficacy Analyses

The Modified Intent-to-Treat (mITT) population will be used for the efficacy analyses.

Participants who have not initiated the study drug infusion, or who do not have a baseline pain intensity score nor any post-dose pain intensity score will be excluded from the mITT population.

- To assess the robustness of the efficacy analyses, additional sensitivity analyses will be performed for the Per-Protocol (PP) population who completed at least 6 hours of study drug infusion, who have safety and efficacy data at least until Time 6 hours, and do not have any significant protocol deviations and for the Full Analysis Set (FAS) population who meet major inclusion/exclusion criteria, who have initiated study drug infusion, and who have any efficacy data after randomization.
- The primary efficacy endpoint is the time-weighted Sum of Pain Intensity Difference (SPID) for the first 12 hours postdose. The SPID for 12 hours postdose (SPID 12) will be estimated using the lineartrapezoidal rule (L x Hour) with the PI scores assigned from Time 0 to Time 12 hours postdose. SPID 12 will be summarized using descriptive statistics by treatment group, and analyzed using an analysis of variance (ANOVA) model with treatment as a main effect. The treatment effect will be tested at a two-sided alpha=0.05 level of significance. The means, standard error (SE), two-sided 95% confidence interval, and two-sided p-value from the ANOVA model will be presented. If the normality assumption is not met using Shapiro-Wilk test, a ranked ANOVA will be used to analyze the primary efficacy endpoint. The rank of the SPID 12 ranked across both treatment arms will be analyzed using a ranked ANOVA model with treatment as the main effect.

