- g. When scheduled for the same time point, assessments will be recommended to be performed in the following order: NRS Vital signs Oxygen saturation via pulse oximetry 12-lead ECG PK sampling Blood sampling for clinical laboratory evaluations. The order of study assessments is allowed to make changes depending on study site circumstances.
 - * It is allowed to use 12-lead electrocardiogram results within 30 days in the absence of medical history.
 - * It is allowed to perform the electrocardiogram and oxygen saturation at Time 10 hours within \pm 2 hours of the scheduled time point.
- h. Pain intensity (NRS, 0-10) will be assessed for 48 hours postdose. Additional pain intensity will be assessed immediately before administration of any rescue medication, and both the NRS and corresponding time will be recorded.
- i. Pharmacokinetic (PK) samples will be collected from the opposite arm to the study drug infusion. If the blood sampling is not available from the opposite arm, the venipuncture is performed from other body parts except for the infusion arm.
- j. A PK sample at Time 0.5 h will be collected before the completion of the loading dose infusion (-5 minutes).
- k. A PK sample at Time 10 h will be collected before the completion of the maintenance dose infusion (-15 minutes). If the total duration of the study drug infusion is less or more than 10 hours, PK sampling at Time 10 h will be performed within 15 minutes before the completion of the infusion. Additional PK samples will be collected 30 minutes after termination of the study drug infusion (±5 minutes).
- Subjects with pain intensity scores of ≥5 on the NRS upon emergence from anesthesia will be randomly assigned to either the VVZ-149 or placebo group (1:1 ratio). Subjects with the initial NRS of <5 will be eligible for randomization once they report the NRS score of ≥5 within 30 minutes after emergence from anesthesia.
- m. Randomized subject will be assigned with a study drug number and and the corresponding study drug will be administered. A continuous IV infusion of VVZ-149 (1,000 mg) or a placebo over 10 hours will be administered as a loading dose of 160 mg for 30 minutes followed by a maintenance dose of 840 mg for 9.5 hours.

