- n. Subjects will be provided with a PCA pump for fentanyl IV infusion upon emergence from anesthesia. Once the study drug infusion has been initiated, subjects may self-administer fentanyl (5 μg IV bolus, 10-min lock-out) by pushing a button of the PCA pump for pain control.
- o. If subjects request additional rescue medications in addition to the PCA opioid, the pain intensity and corresponding time will be recorded. Upon confirming the criteria for rescue medication administration, subjects will be provided with rescue opioid within 15 minutes of the pain intensity assessment using the NRS.
- p. Adverse events identified before the study drug infusion will be documented as medical history.
- q. Safety follow-up will be conducted over the phone. If clinically significant adverse events are reported at the safety follow-up, subjects will be allowed to return to the site for the postoperative standard of care follow-up as necessary and will receive clinical laboratory evaluations, physical examination, and/or vital signs examination.
- r. The HADS and PCS questionnaires can be performed on the day before surgery (Day-1) depending on study site.

10 Version Date: Jan. 27, 2023

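### Does SPID 12 need a stated rule, and a sensitivity analysis, for pain scores taken after rescue?

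*Combined protocol and SAP*

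**What the plan says.** Efficacy Endpoints gives the primary endpoint as "Time-weighted Sum of Pain Intensity Difference (SPID) from baseline over 12 hours after the start of the study drug infusion". Under Statistical Analysis, Efficacy Analyses, it is computed by the linear trapezoidal rule "with the PI scores assigned from Time 0 to Time 12 hours postdose". It is tested by ANOVA with treatment as the only term, or by ranked ANOVA if normality fails. For robustness, "additional sensitivity analyses will be performed for the Per-Protocol (PP) population" and also for the FAS.

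The Rescue medication section opens rescue to subjects who score 5 or more "on the NRS and require additional analgesia in addition to PCA". Footnote h of the Schedule of Assessments adds: "Additional pain intensity will be assessed immediately before administration of any rescue medication, and both the NRS and corresponding time will be recorded". Footnote o says that once the criteria are confirmed, "subjects will be provided with rescue opioid within 15 minutes of the pain intensity assessment using the NRS".

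Rescue is also an outcome. A secondary endpoint is "Total amount of PCA and rescue medication consumption for 12 hours post-dose". Exploratory endpoints include the proportion with no rescue request in 0-2, 2-6 and 6-12 hours, and time to the first and second rescue.

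**The concern.** The word *assigned* suggests a convention for each score, but the document gives none for scores that follow rescue. At least three readings are possible: scheduled scores as observed, observed scores plus the timed pre-rescue scores as extra points, or post-rescue scores replaced by the pre-rescue value. These can give one subject very different SPID 12 values. Changing the analysis set to PP or FAS does not show how much the result depends on the choice.

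The imbalance is plausible. The introductory account of earlier trials reports effective analgesia "with substantially reduced opioid consumption compared to the placebo". If that meant more rescue on placebo here, relief from rescue would be credited to placebo and the SPID 12 difference would move toward zero. The rescue endpoints would show that rescue differed, but not how far SPID 12 moved. The pre-rescue scores are already collected, so a further analysis looks almost free.

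**Working it through.** **Inputs.** From the document: NRS at 0, 0.5, 1, 2, 4, 6, 8, 10 and 12 h; 300 subjects, 1:1; two-sided alpha 0.05. It gives no rescue rate, SPID 12 SD or effect size, so there is no plan figure to reproduce on this point. All other inputs below are assumptions.

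**1. Weight of one score.** An interior score has weight (next time − previous time)/2; each end score has half its adjoining interval. The weights are 0.25, 0.5, 0.75, 1.5, 2, 2, 2, 2 and 1 h, which sum to 12. A score at 4, 6, 8 or 10 h lowered by 1 point through rescue raises that subject's SPID 12 by 2 NRS x h.

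**2. One hypothetical subject.** Baseline 7; later scheduled scores 6, 6, 5, 4, 4, 3, 3, 3; rescue at 0.75 h and 3 h, each with a pre-rescue score of 7. The observed differences are 1, 1, 2, 3, 3, 4, 4, 4, so

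SPID 12 = 0.5(1) + 0.75(1) + 1.5(2) + 2(3) + 2(3) + 2(4) + 2(4) + 1(4) = 36.25.

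| Rule | SPID 12 |
|---|---|
| Scheduled scores as observed | 36.25 |
| Pre-rescue scores added as points | 33.5 |
| Pre-rescue score carried 1 h, then 2 h | 28.4 |
| Carried 2 h, then 4 h | 20.4 |
| First one carried to 12 h | 0.4 |

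Adding the timed points changes little (36.25 − 33.5 = 2.75). The large differences come from replacing observed scores, which the document nowhere says it does.

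**3. Arm difference when both arms request rescue alike at a given pain score.** Simulation, 21 scenarios: effect 0.6 points; pain settling toward a mean of 3.0, 3.8 or 4.6; request probability 10-30% per hour at NRS 5 or more; relief of 1-3 points; no PCA in the model. Change relative to the difference without rescue:

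| Version | Change |
|---|---|
| Observed | −3% to −38% |
| Timed points added | −2% to −32% |
| Carried 1 h | −1% to −26% |
| Carried 2 h | +1% to −16% |
| Carried 4 h | 0% to +6% |

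One example: 6.79 without rescue and 5.49 observed, so (5.49 − 6.79)/6.79 = −19%. With no drug effect, every version rejected in 4.8-5.7% of trials (Monte Carlo SE 0.4 points).

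**4. Arm difference when rescue rates are set by arm, not by pain.** Simulation of 1,500 trials with 150 per arm: effect 0.5 points or none, one rescue per rescued subject, relief 1.5 points for 4 h, carry window 4 h. Without rescue, and before any floor effect, the difference would be 0.5 x (12 − 0.25) = 5.875. Cells give the mean difference in NRS x h, with the two-sided rejection rate in brackets for zero effect.

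| Rescued, VVZ-149 / placebo | Effect 0.5, observed | Effect 0.5, carried | Zero effect, observed | Zero effect, carried |
|---|---|---|---|---|
| 60% / 60% | 5.42 | 4.42 | 0.03 (5.1%) | 0.05 (5.0%) |
| 50% / 70% | 4.45 | 6.40 | −1.05 (7.5%) | 1.76 (16.6%) |
| 40% / 80% | 3.42 | 8.31 | −2.29 (21.1%) | 3.32 (48.4%) |

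The carried version runs from 4.42/5.875 = 0.75 to 8.31/5.875 = 1.41, that is −25% to +41%. At zero effect its error favours the drug. The error of observed scores goes against it.

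In a model like step 3 with the request rate on VVZ-149 halved at the same pain, the 4 h carry overshot the no-rescue difference by 23-34%. At zero effect it gave a false 1.5-2.1 NRS x h in favour of drug; observed scores gave −0.6 to −2.0. The +6% in step 3 is therefore not a bound.

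**The case for a change.** The strongest case for a change is that this is a pivotal primary endpoint and one derivation step is not written down. An unwritten rule leaves a choice. In a null simulation with assumed inputs (2,000 trials, 150 per arm), observed scores rejected 5.0% of the time, while taking the best of observed and the 1, 2 and 4 h carried versions rejected 10.3%. One sentence would close that off, and the extra analysis needs no new data.

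Part of this stands. The document reviewed has no such sentence, and a declared convention is better than an implied one. But the 10.3% needs an analyst to pick among four versions after seeing the results. The text offers no carried version to pick, and its plain reading is the observed scores. The document is also a synopsis that cites an Appendix 16.1 not included in it, so silence here does not show that a fuller SAP is silent.

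The argument from earlier trials is weaker than it looks. The opioid reduction reported there does not separate rescue from PCA, and those infusions ran before, during and after surgery. Here infusion starts after emergence. More rescue on placebo is possible but not established.

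The extra analysis would not isolate the drug effect either. Every subject has PCA fentanyl, whose relief enters the observed scores in the same way, and no score is specified before a PCA bolus. Somnolence is listed among the most frequent adverse events, so unequal requesting at equal pain cannot be excluded. That is the condition under which carrying forward misleads.

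**Conclusion.** No change is needed. The gap is one of missing detail that analysts would fill sensibly: taken literally, SPID 12 uses observed scores regardless of rescue, which is a sound treatment-policy comparison of randomized arms. If placebo takes more rescue, the comparison is conservative. If VVZ-149 takes more, the opioid-amount, rescue-free and time-to-rescue analyses would show it.

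The shrinkage from rescue cannot be derived from the document. With the assumed inputs it was 3-38% when requests depend only on pain, and up to 1 − 3.42/5.875 = 42% when rescue was fixed at 40% versus 80%. That is a property of the question the endpoint asks, not an error in answering it. A carry-forward analysis would exchange it for an error of unknown size that can favour the drug, and its window is one on which reasonable statisticians would disagree. Whether timed pre-rescue scores enter the trapezoid matters less (−2% to −32% against −3% to −38% in the same scenarios) and is an ordinary programming convention.

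This conclusion assumes that no rule replacing post-rescue scores exists in a fuller SAP. If one does, it should be judged on its own terms.
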